**ORIGINAL (in-person) COHORT:**

Summary of overall study findings at completion of study will be shared with participants. During the course of the study, only the i-STAND group will receive feedback charts (showing their

activPAL data). Both groups may receive materials from the group they were not randomized to if they request. Neither group will receive printouts of their HbA1c (or blood glucose\*) levels as these are for data purposes only and are not clinically relevant. As noted in the description of the visit procedures, if participants inquire about their blood values or blood pressure, we will share the information with them but without interpretation and advise them to see their provider if they have questions or concerns. If there are abnormal results, as stated in the consent form, "...if results are out of range, we will contact the study physician on call and confirm that there are no irregularities of concern. You may be advised to contact your primary care provider after the visit if there is a concern."

(\*This applies to those who previously had blood glucose tested prior to removal of this as a measurement item in early 2020.)

**REMOTE (phone) COHORT:**

Summary of overall study findings at completion of study will be shared with participants. During the course of the study, only the i-STAND group will receive feedback charts (showing their activPAL data). Both groups may receive materials from the group they were not randomized to if they request. As noted in the description of the visit procedures, if participants inquire about their blood pressure, we will advise them to see their provider if they have questions or concerns. If there are abnormal results, as stated in the consent form, "...if results are out of range, we will contact the study physician on call and confirm that there are no irregularities of concern. You may be advised to contact your primary care provider after the visit if there is a concern."

**c. Data and/or Specimen Banking**

Indicate if specimens may be used for future research and whether that may include genetic research.

State if data or specimens will be sent to a separate repository. If data or specimens will be banked in a repository for future use as part of this protocol submission address the following questions:

- What will be banked and what identifiers will be associated with the data or specimens?
- Where and how will the data or specimens be stored?
- For what purpose will the data or specimens be used?
- How will the data or specimens be accessed, and who will have access?
- Describe the procedures to release data or specimens, including the process to request a release, approvals required for release, who can obtain data or specimens, and the data to be provided with specimens.

Not applicable

**6. Privacy, Confidentiality and Data Security**

Describe the steps that will be taken to protect subjects' privacy during recruitment, consent and study procedures.

**ORIGINAL (in-person) COHORT:**

- Letters: Letters will be addressed only to participant with "confidential" marked clearly on envelope

- Emails will be sent if requested by the participant for the purposes of scheduling a visit/coaching call or sending a reminder about a visit/coaching call. Any emails sent with program materials will include a reminder not to discuss personal information in a response. If a feedback chart is emailed by request to an i-STAND participant, it will be sent via encrypted email and participants will be given instructions (included in this IRB mod) on how to decrypt that email.
- Phone calls will only occur with those participants who have not opted out of being reached (per their letter, they will be provided with an opt-out number). If the participant is not home, staff member will call again when they can speak with participant.
- In-person written consent will take place in the privacy of a clinic room at the downtown Seattle Kaiser Research Institute
- All in-person sessions will be private (not group-based)
- Study participation will not be documented in EMR\*
- File destruction will occur no later than 5 years from the end of the study or June 1, 2028.

\* If a participant is found to have out-of-range blood pressure or blood draw readings during a measurement visit, the RS may contact the staff MD on call and/or the KP Consulting Nurse Service. In this event, the nurse service may make a note in the participant's medical record of the out-of-range reading. If the MD on call determines the measurement is of particular concern, s/he may notify the participant's provider as outlined on page 3 of the study DSMP.

**REMOTE (phone) COHORT:**

- Letters: Letters will be addressed only to participant with "confidential" marked clearly on envelope
- Emails will be sent if requested by the participant for the purposes of scheduling a visit/coaching call or sending a reminder about a visit/coaching call. Any emails sent with program materials will include a reminder not to discuss personal information in a response. If a feedback chart is emailed by request to an i-STAND participant, it will be sent via encrypted email and participants will be given instructions (included in this IRB mod) on how to decrypt that email.
- Phone calls will only occur with those participants who have not opted out of being reached (per their letter, they will be provided with an opt-out number). If the participant is not home, staff member will call again when they can speak with participant.
- All phone sessions will be private (not group-based)
- Study participation will not be documented in EMR\*
- File destruction will occur no later than 5 years from the end of the study or June 1, 2028.
- If using e-consent: The completed PDFs are in the REDCap File Repository (located behind KP firewall) under "PDF Survey Archive." Files can be downloaded as individual records or bundles in a ZIP file. Note: only users with 'Full data set' data export privileges will be able to download the archived files. The e-Consent Framework also records the IP address of the participant and displays this information in the file repository in order to help regulate potential duplicate forms from a single IP address. PDFs will be downloaded to the G drive so that we can retain copies per the study for up to 5 years. When the study ends, we will delete the REDCap files.

\* If a participant is found to have out-of-range blood pressure during a measurement visit, the RS may contact the staff MD on call and/or the KP Consulting Nurse Service. In this event, the nurse service may make a note in the participant's medical record of the out-of-range reading. If the MD on call determines the measurement is of particular concern, s/he may notify the participant's provider as outlined on page 3 of the study DSMP.

a. Describe the plan for storage of data and/or specimens.

- Who will have access and how.
- Where the data/materials will be stored and for how long.
- What identifiers will be included.
- Any other steps that will be taken to ensure security (e.g., training of staff, authorization of access, password protection, encryption, physical security, and separation of identifiers from data and specimens, certificates of confidentiality).
- Describe the plan to deidentify data, destroy data, or retain/archive data at the end of the study.

Data Security: Only study staff that need to know will be able to access identifiable information about the human subjects. This includes research support specialists working with subjects, project managers, [name], [name] and [name], and health coaches. All data containing identifying information will be kept on password-protected computers using password-protected files. Outcomes data will be stored in a separate file for data analysis and no personally identifiable information will be kept in that file; instead we will use unique study identifiers.

In addition, we will collect adherence data (tracking completion of the in-person session and phone calls) for both intervention groups as well as additional inclinometer (activPAL) data from the i-STAND intervention group. We will audio-record phone sessions to be used in monitoring treatment fidelity.

The likelihood of breach of confidentiality is minimal, as outcome-oriented study data are identified only by study ID and files are password protected. Hard copies, audio files, and tracking data are retained in secured locations accessible only to project staff with a specific need for access. All KPWHRI staff receive training in the protection of confidentiality of research participants. Participants will be informed of all anticipated risks in the informed consent and provided with verbal and written safety information.

Multiple steps will be taken to protect participant confidentiality. Subjects' personal identities will not appear on any study data forms, and all forms and data files containing personal identifiers will be stored separately in secured files. All study files, including digital audio files of the intervention sessions, will be maintained in a centralized location on the KPWHRI departmental server. Access to the file is password protected and subject to the same security protections as other confidential health plan data. Access to the audio files will be limited to the study health coaches and [name] who will review the tapes for treatment fidelity. Audio files will be deleted as soon as possible after they are coded for fidelity. All staff are trained in appropriate

security protections, computer passwords are changed on a regular basis, and all staff sign annual confidentiality agreements.

i-STAND participants who use Fitness devices will not have those devices linked to a personal account. They will be solely linked to a study-account for the purpose of setting the 15-minute reminders to stand. No PHI will be linked to the device.

b. Collection of data from subjects electronically

If you will collect any data from participants electronically (including email, website, etc.), explain:

- How the data will be collected.
- How the information will be secured (encryption, password protection, etc.; may require consultation with IT department).
- Any risks to the participants' privacy posed by using these methods (describe in consent, as applicable).
- How you will verify the participant's identity.

ORIGINAL (in person) COHORT:

Data Collection:

Electronic data collected as part of this study will include:

- 1) Email addresses will be collected if a participant indicates that they wish to manage scheduling, consent or reminders for visits and calls via email.
- 2) Self-reported survey results, documented in REDcap (input either directly by participants using a tablet or, if participant is not comfortable with the technology, they can provide the responses to the survey questions on paper and it will be entered by the research specialist; the paper copy will be destroyed. Note: we are using an internal version of the REDcap database that exists behind the KPWA firewall which also applies to those consents to be collected online. The completed signed (consent) PDFs are temporarily stored in the REDCap File Repository under "PDF Survey Archive." Only study staff with full access to the REDCap account have access to these files. They will be downloaded to a G Drive folder so we can delete the entire REDCap project once the study is closed. As with other study files, these will be destroyed five years after the study ends as noted throughout this document
- 3) Data provided by the inclinometer (activPAL) worn by participants at key timepoints.

Data from the activPAL is collected by taking the small device, inserting a connecting cord from the device to a KPWHRI computer with activPAL software, downloading the participant's activity record from the previous week and using that record to provide an visual of how much

sedentary time occurred. This will all be done by a research specialist who will receive training in using the activPAL software. The activPAL device and the software for analyzing results are both made by Glasgow, Scotland-based PAL Technologies Ltd.

i-STAND group participants will be asked to wear activPAL activity monitors for five or six (if they get boosters) 1-week periods: baseline, one week after baseline, one week at 3 months post-randomization, one week at midpoint (6 months), one week at 9 months (those receiving boosters only) and at 12 months (follow-up). Healthy living group participants will be asked to wear activPAL activity monitors for four 1-week periods: baseline, 3 months, 6 months, and 12 months (follow-up).

We will also give i-STAND participants the option of wearing activity wristbands and using a portable standing desk. The wristbands provide a mild vibration after 15 minutes of inactivity. Settings will be configured using a generic study team account with no identifiable patient data; participants will not create their own account and no personally identifiable information will be shared with the company making the activity bands, as all bands will be assigned a generic email unattached to a subject name or identification.

Participants can stop wearing the activPAL and activity devices at any time.

Once an activPAL device is returned by a participant, all data from the activPAL devices will be promptly downloaded directly onto KPW computers by a study RS. It will never be stored or shared outside the KP firewall. Data from the activity device will not be downloaded or stored for any reason. Upon return of the device, a study RS will wipe the device, resetting it for future use.

**COVID-19 UPDATE:** Until normal business resumes, activPAL data will be downloaded onto study team member home computers (coaches and RS staff). All staff member personal computers are password protected. In addition, the activPAL data is fully de-identified. Once downloaded from the activPAL device, data will be immediately moved to the KPWHRI shared drive and deleted from personal computers. We have completed a Tech Risk Review which deemed this activity from home, using Secure File Transfer from a home computer to a KPWHRI shared drive is considered low risk.

#### **REMOTE (phone) COHORT:**

Data Collection:

Electronic data collected as part of this study will include:

- 4) Email addresses will be collected if a participant indicates that they wish to manage scheduling and reminders for visits and calls via email.
- 5) Self-reported survey results, documented in REDcap (input either directly by participants using a tablet or, if participant is not comfortable with the technology, they can provide the responses to the survey questions on paper and it will be entered by the research specialist; the paper copy will be destroyed. Note: we are using an internal version of the REDcap

database that exists behind the KPWA firewall.

- 6) Data provided by the inclinometer (activPAL) worn by participants at key timepoints.

Data from the activPAL is collected by taking the small device, inserting a connecting cord from the device to a KPWHRI computer with activPAL software, downloading the participant's activity record from the previous week and using that record to provide an visual of how much sedentary time occurred. This will all be done by a research specialist who will receive training in using the activPAL software. The activPAL device and the software for analyzing results are both made by Glasgow, Scotland-based PAL Technologies Ltd.

i-STAND group participants will be asked to wear activPAL activity monitors for five or six (if they get boosters) 1-week periods: baseline, an optional one week wear 6 weeks after baseline, one week at 3 months post-randomization, one week at midpoint (6 months), another optional one week wear at 9 months (those receiving boosters only) and at 12 months (follow-up). Healthy living group participants will be asked to wear activPAL activity monitors for four 1-week periods: baseline, 3 months, 6 months, and 12 months (follow-up).

**2022 BUDGET CUT UPDATE:** As of March 31, 2022, neither the i-STAND cohort nor the control cohort will have a 12-month assessment. Furthermore, the i-STAND cohort will not be offered the optional wears (6-week and again at 9-months if they were to be re-randomized).

We will also give i-STAND participants the option of wearing activity wristbands and using a portable standing desk. The wristbands provide a mild vibration after 15 minutes of inactivity. Settings will be configured using a generic study team account with no identifiable patient data; participants will not create their own account and no personally identifiable information will be shared with the company making the activity bands, as all bands will be assigned a generic email unattached to a subject name or identification.

Participants can stop wearing the activPAL and activity devices at any time.

Once an activPAL device is returned by a participant, all data from the activPAL devices will be promptly downloaded directly onto KPW computers by a study RS. It will never be stored or shared outside the KP firewall. Data from the activity device will not be downloaded or stored for any reason. Upon return of the device, a study RS will wipe the device, resetting it for future use.

**COVID-19 UPDATE:** Until normal business resumes, activPAL data will be downloaded onto study team member home computers (coaches and RS staff). All staff member personal computers are password protected. In addition, the activPAL data is fully de-identified. Once downloaded from the activPAL device, data will be immediately moved to the KPWHRI shared drive and deleted from personal computers. We have completed a Tech Risk Review which

deemed this activity from home, using Secure File Transfer from a home computer to a KPWHR shared drive is considered low risk.

c. Does this study involve the disclosure of PHI to a collaborator?

If any data will be sent outside of this site, list each recipient (may list by role or category if the information is the same for several different entities). For each recipient, describe:

- What will be sent.
- Whether the information will be fully identifiable (PHI, if health information), a Limited Data Set, de-identified, or aggregate.
- How the data/materials will be transferred securely (for instance, Secure File Transfer).

Not applicable

**7. Provisions to Monitor Data to Ensure the Safety of Subjects**

This is required when research involves more than Minimal Risk to subjects.

The plan might include establishing a data monitoring committee and a plan for reporting data monitoring committee findings to the IRB and the sponsor.

Describe:

- Who will monitor the study data for safety?
- The plan to periodically evaluate the data collected regarding both harms and benefits to determine whether subjects remain safe.
- What data are reviewed, including safety data, untoward events, and efficacy data.
- How the safety information will be collected (e.g., with case report forms, at study visits, by telephone calls with participants).
- The frequency of data collection, including when safety data collection starts.
- The frequency or periodicity of review of cumulative data.
- Criteria for taking action on monitoring findings (for instance, stopping rules, immediate suspension, reporting, protocol changes, changes to monitoring frequency or plan).
- For studies monitored by a DSMB/C, describe the committee membership and structure, meeting format, and quorum requirements. Upload the board/committee charter, if one exists. (This bullet is not applicable)

[name], the PI, will be responsible for notifying the IRB of all adverse events (AEs). All participants learned to be deceased during the course of the study, regardless of the cause of death, will be reported to the IRB. The IRB will work with the PI to ensure additional agencies (e.g., NIH) are notified as required. The IRB will also determine if other immediate action is required (e.g., suspension of recruitment, protocol closure, etc.). Temporary or permanent suspension of an NIH-funded protocol will be reported to the NIH grant program director directly responsible for the grant.

Monitoring of Adverse Events by PI and Project Staff. Project staff (health coaches, research specialists, programmer, etc.) will be trained to identify potential AEs, document events on an adverse event form, and report any events immediately to the study PI and the project manager. [name] will ensure that all AEs are appropriately handled and reported to the IRB and NIH authorities, as appropriate. The project manager will conduct routine protocol compliance

checks to ensure that safety procedures, such as ensuring participant confidentiality and maintaining approved standards for data transport, are strictly adhered to. In the case that the MD on call for the team (either [name] or [name]) and /or the DSM [name], determines that a participants lab values are out of range to an extent that they believe the participants provider should be notified, s/he may contact the provider (see the DSMP protocol) explaining the results of the test (example: high blood pressure). In order to do this, we need to collect the participant's provider name and have added this to the Contact Sheet.

Note: The study physician may determine what method of contacting the provider is most appropriate given the needs of the individual participant.

For the purposes of any Epic messages, only Drs [name] and [name] have Epic access and the only ones who would use this means of contacting a participant's provider.

HIPAA Compliance. All participants will be recruited from KPWA. As such, their participation is subject to the Health Insurance Portability and Accountability Act of 1996 (HIPAA) privacy and security standards. All KPHRI staff have completed required HIPAA training, and all research activities will be conducted in compliance with the HIPAA standards.

Monitoring Data Quality and Integrity. Several procedures will be used to maintain data integrity. All databases will be stored in a centralized location on a departmental server at KPHRI. Data will be backed up daily, and access to any participant information will be password protected and limited to persons working on the project. Project staff will only have access to specific data required for their project tasks. Identifying information will be stored separately from the assessment data. Data will be audited on an ongoing basis by the Project Manager to ensure confidentiality safeguards are being upheld and data integrity is being maintained. Data entry systems will be set up to allow field checks, range checks for continuous variables, valid value checks for categorical variables, and checks for logical consistency of responses. Queries and data reports will be generated on a routine basis to monitor data quality. REDCap data integrity safeguard: we are using the internal version of REDcap which is behind the KPWA firewall.

Data Safety Monitoring Panel. [name] will monitor the study in compliance with IRB-approved procedures. A Data Safety Monitoring Panel, composed of two KPHRI investigators who are not associated with the project, will review all adverse events and make final determinations as to whether any AEs are study related. On a quarterly basis during the course of the trial, the panel will evaluate the adverse event data to protect the safety of the study participants. It will make specific recommendations to the PI and study team regarding modifications to the intervention based on any observed adverse effects of the treatment under study.

## 8. Risks and Benefits

a. Risks to Subjects

List the reasonably foreseeable risks, discomforts, hazards, or inconveniences to the subjects related to the subjects' participation in the research. Describe the probability, magnitude, duration, and reversibility of the risks. Consider physical, psychological, social, legal, and economic risks.

- If applicable, indicate which procedures may have risks to the subjects that are currently unforeseeable.
- If applicable, indicate which procedures may have risks to an embryo or fetus should the subject be or become pregnant.
- If applicable, describe risks to others who are not subjects and risks to Kaiser Permanente

The primary risks of participation include a breach of confidentiality; emotional upset or embarrassment due to participation in the research intervention, in-person measurements, and surveys; and potential adverse events related to participation in the intervention. People may feel uncomfortable wearing small devices that capture movement. The waterproof medical dressing used to secure the activPAL to the top of the thigh could result in skin irritation, though this outcome has rarely been reported in previous studies using activPAL and we use a medical grade adhesive. However, if this occurs, participants can discontinue use, try their other leg, or try a different adhesion method. Participants may feel uncomfortable when having their height and weight measured, performing brief physical function tasks, or completing a survey which asks about psychosocial factors, well-being, and quality of life. Persons who choose to increase their routine physical activity levels could experience physical-activity-related injuries such as pulled muscles or sprains. Participants may experience discomfort and/or local bruising at the site of the capillary finger stick blood draw.

For those participants with high or low blood pressure, the potential improvement in physical health is greater than potential adverse effects from increasing standing time. The goal of the i-STAND intervention is to increase breaks from sitting time. Study physicians do not think these, or any participants, are likely to experience harms greater than those encountered in normal life because standing up is a typical daily activity. Any unanticipated events that do occur will be documented in the AE form. At best, participants may be at increased risk for muscle stiffness/soreness or falls from standing/moving more, but longer term their physical health may benefit from reduced sedentary time.

In the event that a participant presents with any of these symptoms while waiting to be seen for their in-person measurement visit (e.g.: in the waiting room), the RS will follow the "Physical Health Concern Protocol" which entails contacting the KP Consulting Nurse Service, and follow directions from that nurse, and possibly rescheduling the measurement visit for another time.

The likelihood of breach of confidentiality is minimal, as outcome-oriented study data are identified only by study ID and files are password protected. Hard copies, audio files, and tracking data are retained in secured locations accessible only to project staff with a specific need for access. All KPWHRI staff receive training in the protection of confidentiality of research participants. Participants will be informed of all anticipated risks in the informed consent and provided with verbal and written safety information. Per the consent, if a participant's lab values are out of range to an extent that the MD on call ([name] or [name]) believes the participant's provider should be notified, s/he will send a letter (included in the DSMP protocol) to the provider explaining the results of the test (example: high blood pressure).

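### Section 8.a's adverse event sentence is worded more narrowly than section 7, leaving it unclear whether foreseen harms such as falls and soreness go on the form, and no uniform adverse event question is described in either arm

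*Combined protocol and SAP*

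**What the plan says.** Section 8.a (Risks to Subjects) has one sentence on recording: "Any unanticipated events that do occur will be documented in the AE form". The sentence after it says that "participants may be at increased risk for muscle stiffness/soreness or falls from standing/moving more". Earlier in 8.a, people who become more active "could experience physical-activity-related injuries such as pulled muscles or sprains", and skin irritation from the activPAL dressing is listed as a possible effect.

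Section 7 (Provisions to Monitor Data to Ensure the Safety of Subjects) is worded more broadly. Project staff, a group that includes coaches and research specialists, "will be trained to identify potential AEs, document events on an adverse event form, and report any events immediately to the study PI" and to the project manager. The PI notifies the IRB of all adverse events. A two-person panel independent of the project "will review all adverse events and make final determinations as to whether any AEs are study related", evaluates the adverse event data quarterly and may recommend changes to the intervention.

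Three other parts of section 5 (Study Procedures) bear on this. The data sources table lists falls among medical events taken from the health plan's data warehouse (VDW). The blinding paragraph says that coaches are unblinded and the research specialist is blinded. The risk mitigation list refers to a separate DSMP, which is not among the documents.

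**The concern.** There are two linked gaps.

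The first is wording. The only recording sentence in 8.a uses a narrower term than section 7 and stands next to a list of foreseen harms that the term does not naturally cover. A staff member relying on 8.a could reasonably be unsure whether a fall or a strained muscle needs a form.

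The second is ascertainment. The documents describe who recognises and reports adverse events, but no standard question put to every participant. If events come to light in conversation, what is recorded depends on what the conversation is about, and that differs by arm.

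The panel advises on the intervention from recorded events. Participants may be up to 89 years old, and the protocol itself says falls might increase. Foreseen events that are missed, or caught more readily in one arm, make the panel's comparison and any later report of harms less reliable.

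**Working it through.** No figure in the plan is at issue, so the check sets the sections side by side.

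1. **Scope of recording.** Section 8.a covers unanticipated events. Section 7 covers potential adverse events, with no filter by expectedness, then requires IRB notification and panel review of all adverse events. Section 7 is the broader.

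2. **Events in the gap.** Section 8.a foresees falls, muscle stiffness or soreness, pulled muscles, sprains and skin irritation. Each fits section 7's scope if it counts as an adverse event. None is clearly within the 8.a sentence.

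3. **Is there a definition that settles it?** The documents shown define neither an adverse event nor an unanticipated one.

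4. **Is there a standard question?** The visit steps under the Sequential description (Original cohort baseline, month 3 and month 6; Remote cohort baseline, months 3 and 6) list surveys, activPAL, blood pressure, weight, waist and physical function, plus HbA1c in person. The baseline survey includes symptom scales such as pain and fatigue. No adverse event or falls question is listed. Section 7's template asks how and how often safety data are collected; the answer gives staff identification and a quarterly panel review.

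5. **Can capture differ by arm?** The number of coach contacts is matched at 10 per arm, but content is not. i-STAND sessions concern standing, the desk and the prompting band. Control sessions draw on Table 4, which includes Preventing Falls, Chronic Pain and Arthritis & Healthy Joints. Either arm's content could prompt reports of falls or pain.

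6. **What would differential capture do?** If a proportion c1 of events is recorded in i-STAND and c0 in control, the observed ratio of rates is (true ratio) × (c1/c0). The documents give no value for c1, c0 or the true rates, so neither the size nor the sign of any distortion can be derived.

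7. **Is there another route?** VDW data can show falls that reach the health record. That table names no equivalent for soreness, sprains or skin irritation, and nothing says VDW falls go to the panel. Section 5.a (Data Analysis) describes no comparison of adverse events by arm.

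**The case against.** The strongest reply is that section 7, not 8.a, is the operative safety text, and it already requires adverse events to be documented whether expected or not. This stands. A reader might infer that 8.a restricts the form to unanticipated events, or that it contradicts section 7. The documents support neither: 8.a does not say that anticipated events are left off, and staff can follow both sections at once. The sentence also follows a statement that the study physicians expect no harms beyond those of ordinary life, so it may be meant as reassurance and not as a filter.

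A reader might also infer that falls would be invisible, or that i-STAND would show a spurious excess. VDW records give falls a partial second route, and the control topics make the direction of any differential capture unknown.

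It is also fair to say that the DSMP, the adverse event form, the surveys and the call scripts were not available and may already contain a standard question. Research specialists, who are blinded, are among the staff trained to identify events in both arms. These facts limit the point to what the documents shown describe; they do not supply the missing definition or question.

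**Conclusion.** The point holds as a minor one. Section 8.a is narrower than section 7 and leaves the recording of its own foreseen harms unclear. The documents shown also describe no uniform way of asking about adverse events, so capture may be incomplete and may differ by arm in an unknown direction. This is not an established failure of safety recording.

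No numerical size can be given. Any figure for missed falls or a distorted ratio would restate assumed event and capture rates, because the documents contain none. The ascertainment half rests on the assumption that the DSMP and surveys do not already include a standard question. If they do, only the wording mismatch remains.

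**What to change.** 1. In section 8.a, replace the subject of the recording sentence with *All adverse events, anticipated or not, in both arms*, so that it agrees with section 7.

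2. Unless the DSMP or surveys already provide it, add one identical scripted adverse event and falls question, asked by the blinded research specialists in both arms at contacts that already exist. At month 3 this is the packet reminder call in the Original cohort and the phone visit in the Remote cohort; at month 6 it is the measurement visit in both.

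3. For contacts already past, state in the trial report how adverse events were ascertained.

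The cost is one amended sentence, one short question at existing contacts, and more minor events for staff to log and the panel to review.
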